blood vessel. This imaging plane was selected on the vessel of interest at the C1-2 intervertebral level based on arterial visualization on a maximum intensity projection of a 2-dimensional time-of flight MRI angiogram. Magnetic resonance acquisition parameters were as follows: fast gradient recalled echo; echo time/repeat time, 3.9/8.9 milliseconds; flip angle, 20°; 20 cm field of view; 512* 512 matrix; 244-Hz/pixel receiver bandwidth; 1 average; 4 mm thick; and velocity encoding of 50 cm/s encoded for 30 phases per cardiac cycle. Owing to anatomical variations, occasional slices could only approximate orthogonality. All image measurements were obtained by manually selecting the optimal anatomical site between the base of the odontoid process and approximately 1 cm above the tip of the dens. According to Lotz et al vessel obliquity is tolerable to above or equal to 15 degrees, above which will cause a deviation from the true flow.⁴¹ Data capture was triggered by prospective gating using a peripheral pulse (MRI scanner-pulsed oximeter). The image acquisition time for each flow measurement was approximately 1 minute 30 seconds depending on heart rate. Flow analysis was performed using Segment v1.9 software⁴⁷ (Medviso, Lund, Sweden). Dynamic regions of interest were drawn on the left and right vertebral arteries to quantify mean, as well as peak velocities, and flows. Data in the trigger window portion of the cardiac cycle were derived by spline interpolation using Matlab (Mathworks, Natick, MA). The final data set for a complete cardiac cycle, therefore, contained measurements from all the cardiac cycles that elapsed during the scan time. A typical phase-contrast image is presented in Figure 2, with regions of interest (ie, vascular cross sections) labeled. Subsequently, rsMRI BOLD was performed. This was acquired using a gradient echo, echo planar imaging (GE-EPI) sequence (64x64 matrix, 28 axial slices (5mm thick, no skip), 24cm FOV, TE/TR/flip angle = 35ms/2000ms/90°, 180 temporal points, total scan time=6 minutes). During the rsMRI BOLD scan, subjects were asked to keep their eyes open, stay awake, and not think of anything in particular.

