Following the 3D anatomical, rsMRI BOLD, ASL and phase contrast MRI the subject was removed from the MRI and condition 2 and 3 were applied separately in a randomized order. Each condition was immediately followed by realignment of the head, return to the MRI bore, scan of a 3-plane localizer and then ASL, phase contrast, rsMRI BOLD and 3D anatomical scans. The latter three were always performed with the 3D anatomical last seeing as microvascular changes (i.e. blood flow) were more likely to be detected early after the manipulation while structural changes (i.e. 3D scan) wouldn't be expected to occur.

Data Analysis

Data quantification was performed by an experienced analyst who remained blinded to the test maneuvers. ASL blood flow and rsMRI BOLD data were analyzed using analysis of functional neuroimaging (AFNI). Functional rsMRI BOLD data preparation first involved slice timing correction and 3D rigid body motion correction. For each subject all ASL and rsMRI BOLD data were spatially registered to the initial (neutral condition) position. Anatomical, blood flow and functional data were transformed automatically to the Colin27 atlas, using the AFNI command @auto_tlrc, with functional data resampled to a 2mm isometric grid.⁴² Temporal band-pass filtering with cutoffs of $0.009\text{Hz} < f < 0.08\text{Hz}$ was performed in order to suppress unwanted physiological signals and some hardware noise.⁴³ Functional connectivity within the default mode network (DMN) was assessed using the AFNI plugin InstaCorr, a seed-based approach, which uses the Pearson

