method of correlation to compare time signals.⁴⁴ The DMN is the most dominant temporally correlated resting network in the awake brain, defined as regions positively correlated in time with the posterior cingulate cortex (PCC) seed voxel. The PCC was defined automatically using the AFNI Talairach method ‘Talairach to’ and selecting a single voxel from each the left and right PCC for one analysis (ColinN27 coordinates: 10, 54, 14, and -10, 54, 14). These were both subsequently fused in the post-processing. A 5mm FWHM Gaussian spatial smoothing filter was applied for maximize likelihood of overlap with inter-subject group analysis. Also, temporal outliers determined with the AFNI function 3dToutcount were censored out. The ASL cerebral blood flow data was analyzed similar to rsMRI BOLD in that following spatial co-registration to the neutral condition and spatial blurring with a 5mm FWHM Gaussian convolution kernel, ASL data was warped to the N27 atlas. Group analysis was accomplished using a 1-way within subject 3D-ANOVA, with the one factor being neck position. Post hoc testing included contrasts between neutral, maximum voluntary rotation and CSM, and also a contrast between maximum voluntary rotation and CSM. Statistical significance was defined as anything lower than an alpha value of 0.05.

Mean and SDs were calculated for VA blood velocity, flow, peak velocity, and peak flow for each of the head conditions and VA side. Differences between task maneuvers and VA flow and velocity were evaluated using a repeated-measures analysis of variance with factors of head position and VA side, and a level of significance was set at .05, using R-project version 2.12.1 (R Development Core Team, 2010. R: A language and environment for statistical computing. R Foundation for Statistical Computing, Vienna, Austria. ISBN 3-900051-07-0, URL <http://www.R-project.org/>).

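### The BOLD band-pass filter can only partly suppress physiological noise at a TR of 2 s, and no motion, tissue or physiological regressors are described to deal with the rest.

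*Combined protocol and SAP*

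**What the plan says.** The Magnetic Resonance Imaging Protocols section gives the BOLD acquisition as "TE/TR/flip angle = 35ms/2000ms/90°, 180 temporal points, total scan time=6 minutes", in 28 slices. The head is held with sponges. A pulse oximeter is mentioned only for the phase-contrast flow scan: "Data capture was triggered by prospective gating using a peripheral pulse (MRI scanner-pulsed oximeter". No use of it is stated for BOLD.

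In Data Analysis, "Functional rsMRI BOLD data preparation first involved slice timing correction and 3D rigid body motion correction". Registration to the neutral scan and warping to an atlas follow. The 0.009-0.08 Hz filter comes next; it "was performed in order to suppress unwanted physiological signals and some hardware noise". After that come 5 mm smoothing and a censoring step: "temporal outliers determined with the AFNI function 3dToutcount were censored out". No censoring threshold is given.

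For the outcome itself, "Functional connectivity within the default mode network (DMN) was assessed using the AFNI plugin InstaCorr, a seed-based approach". It uses Pearson correlation with single-voxel seeds in the left and right posterior cingulate. Group comparison is a one-way within-subject ANOVA on neck position. The neutral scan always comes first; only the order of rotation and manipulation is randomized.

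The text mentions no motion-parameter, white-matter, CSF or recording-based physiological regressors. It also does not say that they were left out.

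**The concern.** A band-pass filter removes only what lies outside its band after sampling. At this TR the heartbeat is sampled too slowly to be seen at its own frequency, and it reappears at a lower one. If that lower frequency is between 0.009 and 0.08 Hz, the filter keeps it. Realignment moves volumes back into register but does not remove signal changes caused by motion. Censoring drops outlying volumes and does not touch a continuous oscillation.

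The residual noise goes straight into the seed correlations and then into the neck-position contrasts. Whether cardiac signal falls in the band depends on heart rate, so it need not cancel within a person. Because neutral is always scanned first, settling of heart rate or growing restlessness over the roughly 60-minute session would line up with the contrasts against neutral. A change in noise could then be read as a change in connectivity.

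**Working it through.** **Inputs from the documents:** TR 2000 ms, 180 volumes, 6 minutes, 28 slices; pass band 0.009-0.08 Hz. **Assumption:** heart rate of 50-100 beats/min, since the documents give no heart rates.

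**1. The plan's own figure.** 180 × 2 s = 360 s = 6.0 min. This agrees with the stated scan time, so TR = 2 s is consistent.

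**2. Sampling limit.** Sampling rate = 1/2 s = 0.5 Hz, so the Nyquist limit is 0.25 Hz, or 15 cycles/min. Any realistic heart rate is aliased.

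**3. Aliased frequency.** With f = heart rate/60, alias = |f − 0.5 × round(f/0.5)|.

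| Beats/min | f (Hz) | Alias (Hz) | In 0.009-0.08 Hz? |
|---|---|---|---|
| 58 | 0.967 | 0.033 | yes |
| 60 | 1.000 | 0.000 | no |
| 62 | 1.033 | 0.033 | yes |
| 70 | 1.167 | 0.167 | no |
| 75 | 1.250 | 0.250 | no |
| 80 | 1.333 | 0.167 | no |
| 88 | 1.467 | 0.033 | yes |
| 92 | 1.533 | 0.033 | yes |

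**4. Heart rates that leak.** The band edges are 0.009 × 60 = 0.54 and 0.08 × 60 = 4.8 beats/min either side of 60 and of 90. This gives 55.2-59.5, 60.5-64.8, 85.2-89.5 and 90.5-94.8, each 4.26 wide. Share of a uniform 50-100 range: 4 × 4.26/50 = 34%. Counting the second harmonic, which adds mainly 72.6-74.7 and 75.3-77.4, the share is 45%.

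**5. Sensitivity to the heart-rate assumption.** If mean heart rates are normally distributed, the share of participants with the fundamental in band is 66% (mean 60, SD 4), 26% (70, SD 10), 23% (75, SD 10) or 4% (75, SD 5).

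**6. Power left after filtering.** I simulated 180 volumes at 2 s with a slow heart-rate drift of SD 3 beats/min (assumed). About 68-69% of cardiac-fundamental power stays in band at 58, 62, 88 or 92 beats/min, against 3.6% at 70 and 0.4% at 75.

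**7. Respiration.** The fundamental is out of band from 4.8 to about 25.2 breaths/min. Its second harmonic is in band at about 12.6-14.7 and 15.3-17.4 breaths/min.

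**8. Direction of the distortion.** If the 28 slices are spread evenly over the TR, neighbours in acquisition order are 2/28 = 0.071 s apart. At 60 beats/min that is 0.071 × 360° ≈ 26° of cardiac phase, and one volume spans two beats. Aliased cardiac signal therefore differs in phase between slices and can push a seed correlation up or down.

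**9. Cost of the regressors.** Effective degrees of freedom after filtering are about 2 × (0.08 − 0.009) Hz × 360 s = 51, before censoring. Six motion terms plus white-matter and CSF means make 8, leaving about 43. The standard error of a Fisher-transformed correlation goes from 1/√48 = 0.144 to 1/√40 = 0.158, about 10% larger per scan.

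**The case against.** The other side has real substance. The plan claims suppression, not elimination, and the filter does suppress: it removes slow drift, the usual respiratory fundamental, and the cardiac fundamental between about 64.8 and 85.2 beats/min. Sponges, realignment and outlier censoring all bear on motion. The analyst was blinded. BOLD follows the ASL and phase-contrast scans, so it is not acquired straight after the manoeuvre. The vertebral artery flow and ASL analyses do not use this filter. All of that stands.

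A reader might infer more than the documents support:

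- **That cardiac signal generally folds into the pass band.** It does so only at particular heart rates, and none are reported.
- **That no nuisance regressors were used.** The text is a short methods summary and is silent; it shows only that none are described.
- **That shared noise inflates connectivity.** Slice-dependent phase means that aliased cardiac signal distorts correlations in either direction.
- **That manipulation produces a false effect.** That would need a systematic shift in heart rate or motion between conditions. Unsystematic changes mainly add noise to the within-subject ANOVA.

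One could also say that the choice of regressors is a matter of pipeline preference, and that tissue averages do not model slice-dependent cardiac phase directly. The second part is fair and limits what the fix can promise. Neither part removes the gap: as listed, the pipeline leaves residual motion variance and, at some heart rates, cardiac variance in the correlations.

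**Conclusion.** The concern holds in limited form. The filter is the only listed step aimed at physiological noise, and at TR 2 s it cannot remove cardiac signal that aliases into 0.009-0.08 Hz. This happens over 34% of an assumed uniform 50-100 beats/min range; under the normal distributions tried above, the share runs from 4% to 66%. Residual motion variance is also left, with no described step to remove it.

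The aliasing result rests only on the stated TR and cutoffs. The shares rest on assumed heart rates. The size of any bias in the neck-position contrasts cannot be judged from the documents, and no such bias has been shown. Only DMN connectivity is touched. The change is worth making because it is cheap and standard, not because the present result is known to be wrong.

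**What to change.** State whether any nuisance regressors were used. If not, fit one regression per BOLD scan before computing seed correlations, containing:

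- the six motion parameters already estimated in rigid-body correction;
- mean white-matter and mean CSF signals;
- the band-pass terms;
- the censored volumes, with the 3dToutcount threshold stated.

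Compute the seed correlations from its residuals. These terms reduce aliased cardiac signal without guaranteeing its removal, so describe the filter as giving partial suppression of physiological signal. If pulse-oximeter traces were saved during BOLD, report heart rate by condition, so that readers can see whether it shifted and whether it lay in a leaking range.

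The cost is a pipeline re-run on existing data and about 8 of roughly 51 effective degrees of freedom per scan.

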After each condition, MRI of the cerebrum and upper neck for blood flow ensued. The total time elapsed for each participant testing protocol was 60 minutes. The total time elapsed for each condition was approximately 20 minutes. This included applying the condition (1 minute), replacing the participant back into the MRI bore (approximately 1 minute), and routine image sequencing (approximately 18 minutes). Estimates of repeatability of flow measures were made in preliminary work by quantifying VA flow in a single healthy participant twice over a 2-month interval.

A practitioner with more than 30 years of practice experience conducted the upper cervical manipulation.³²⁻³⁴ The manipulation procedure required no transfer of the participant; rather, it was performed on the adjustable and pivotal MRI bed in the MRI room with the participant in the supine position (Fig 1). The procedure was a high velocity, low amplitude (HVLA) impulse, designed to initially position the participants' heads in an axial rotation, flexion as well as lateral flexion postures. Variations of head positions between operators have been demonstrated to be relatively small.^{35,36} The clinician performed the procedures in representative manner, first establishing the end range of motion to determine appropriate preload position for the manipulation before applying a typical clinical force impulse in the coronal plane with minimal traction component. Before the delivery of each maneuver, the participants were queried on their comfort, condition, and willingness to continue.

A brief 5-item analogue scale was administered to each of the participants and clinician immediately after the test maneuvers. This scale provides quantitative estimates of the patient's and operator's judgment of the descriptive characteristics of the CSM procedure on a continuous scale of 0 to 10. The words "fast," "force," "comfort," "confidence," and "precise" were used as descriptors as validated and used in several other studies.³⁷⁻³⁹ The scale provided a means of contrasting the procedure characteristics within the context of the range of typical performance, as represented within the literature.

Magnetic Resonance Imaging Protocols

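### Neutral is always the first scan, so the two neutral contrasts and the omnibus test cannot be attributed to neck position; only manipulation versus rotation is randomised

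*Combined protocol and SAP*

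**What the plan says.** **Order of conditions.** The Magnetic Resonance Imaging Protocols section describes one full set of scans before any manoeuvre: "Following the 3D anatomical, rsMRI BOLD, ASL and phase contrast MRI the subject was removed from the MRI". After that, "condition 2 and 3 were applied separately in a randomized order". Data Analysis confirms which scan came first: "all ASL and rsMRI BOLD data were spatially registered to the initial (neutral condition) position".

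**Timing.** Test Protocols gives about 20 minutes per condition and adds: "The total time elapsed for each participant testing protocol was 60 minutes".

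**Series order.** The neutral block is listed with the anatomical scan first. After each manoeuvre the order is "scan of a 3-plane localizer and then ASL, phase contrast, rsMRI BOLD and 3D anatomical scans", so the anatomical scan comes last.

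**Models.** For perfusion and BOLD data: "Group analysis was accomplished using a 1-way within subject 3D-ANOVA, with the one factor being neck position". Post hoc contrasts compare neutral with each manoeuvre and the two manoeuvres with each other, at 0.05. VA flow and velocity use a repeated-measures ANOVA with head position and VA side, also at 0.05. Neither model has a period or sequence term, and no limit is placed on how the neutral contrasts are to be read.

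**The concern.** Test Protocols calls neutral a control, and both models treat it as one level of a position factor, on the same footing as the two randomised conditions. It is not on that footing. Whatever changes between the first scan and the later ones, for reasons unrelated to the manoeuvre, enters both neutral contrasts in full. It also enters the omnibus test, or the position main effect in the VA model.

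At stake is whether a significant change from neutral after manipulation can be called an effect of manipulation. On this design it cannot. A smaller, separate matter is that the one randomised comparison is analysed without regard to which manoeuvre came first.

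**Working it through.** **1. How many neutral scans?** Test Protocols is loosely worded: it can be read as neutral before each manoeuvre, and its allocation sentence reads like parallel groups. The imaging section describes one initial block and then both manoeuvres in random order. Timing agrees: 1 min manoeuvre + 1 min return + 18 min scanning = 20 min, and 3 × 20 = 60 min. There is no room for a repeat neutral block.

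**2. Identifiability.** The indicator for neutral and the indicator for scan 1 are the same column. With 20 participant columns, 2 for condition and 2 for scan position, the design matrix has 24 columns and rank 23. If period is coded 0 for neutral and −0.5/+0.5 for the first/second post-manoeuvre scan, there are 23 columns and rank 23. Period can thus be adjusted for in manipulation versus rotation, but no added term recovers the neutral effect itself.

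**3. Series order.** The anatomical scan precedes the flow scans in the neutral block and follows them later. Its duration is not stated. The stated series times are 0.5 (perfusion) + 1.5 (phase contrast) + 6 (BOLD) = 8 min of about 18, so it takes less than about 10 min. Whether BOLD also preceded perfusion in the neutral block is unclear: one list suggests it did, while the series description places it after phase contrast ("Subsequently, rsMRI BOLD was performed").

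**4. Illustration for the neutral contrasts.** The plan has no power figure to reproduce. Its only repeatability data are one healthy participant measured twice over 2 months, so the shift δ is an assumption. Units are paired-difference SDs; n = 20, two-sided 0.05, no manoeuvre effect, independent scan errors, single test.

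- Paired t, 19 df: noncentrality = δ√20.
- Omnibus F(2, 38), means (0, δ, δ), single-scan variance 0.5: noncentrality = 20 × (2/3)δ² / 0.5 = 26.67δ².

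| δ | t noncentrality | each neutral contrast | F noncentrality | omnibus |
|---|---|---|---|---|
| 0.1 | 0.447 | 7.1% | 0.267 | 6.9% |
| 0.2 | 0.894 | 13.6% | 1.067 | 13.2% |
| 0.3 | 1.342 | 24.7% | 2.400 | 24.6% |
| 0.5 | 2.236 | 56.5% | 6.667 | 59.6% |

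In simulation the VA position main effect behaves like the omnibus (7, 13, 24–25, 60%). The position × side interaction stays at about 5% when drift is equal on both sides.

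**5. Period term for manipulation versus rotation.** The assumed effect is 0.66 paired-difference SD (80% power without drift). Drift is now between the two post-manoeuvre scans. Simulated power of the paired test, without / with period:

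| drift | 10/10 split | simple randomisation (assumed) |
|---|---|---|
| 0 | 80.0 / 79.7 | 80.2 / 77.7 |
| 0.1 | 79.5 / 79.5 | 79.7 / 77.7 |
| 0.2 | 78.9 / 79.8 | 78.4 / 77.4 |
| 0.3 | 77.2 / 79.6 | 76.5 / 77.5 |
| 0.5 | 72.2 / 79.7 | 70.9 / 77.6 |

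Without the term, average type I error under simple randomisation stays near 5%. In a trial with an uneven split, the estimate is biased by drift × (difference in sequence sizes)/20. At 7/13 that is 6/20 = 0.3 of the drift. For Binomial(20, 0.5), a split of 7/13 or worse has probability 0.26.

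**The case against.** - **Neutral first is a natural baseline.** That may be a sound choice. It still makes the contrast a before-after change, which is all that is asked to be stated.
- **Existing safeguards.** Rotation shares removal, repositioning, return to the bore and series order with manipulation, and that contrast is already planned. Head position was standardised with markers and the analyst was blinded. This stands, and it is why manipulation versus rotation should carry the inference. None of it frees the neutral contrasts from scan 1.
- **The VA model has an internal check.** Position × side is protected if drift is equal on both sides. This stands, as a partial check under that assumption.
- **Drift is unknown and the rates are for single tests.** Correct. The percentages are not estimates for this trial or image-level rates for the voxelwise analysis. The aliasing does not depend on them.
- **The period term is close to a preference.** Its gain is small, or a loss, at low drift. This is why it is secondary and the unadjusted result should be shown as well.

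Three stronger readings are tempting but unsupported. First, a reader might take "microvascular changes (i.e. blood flow) were more likely to be detected early after the manipulation" as the plan's own admission of drift from scan 1. It concerns time since a manoeuvre, and none precedes the neutral scan. Second, one might infer that the missing period term inflates false positives for the randomised contrast. On average it does not for the paired test; the bias arises only with drift and an uneven split. Third, one might say the plan claims a causal effect against neutral. It does not say so; it only leaves that reading open.

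**Conclusion.** The point holds and should be fixed. Both neutral contrasts and the neutral-versus-later degree of freedom of the omnibus test are fully aliased with scan 1, so significance there cannot be attributed to neck position. This follows from the design without any drift assumption. Its numerical size is unknown: false-positive rates of roughly 7% to 60% correspond to assumed shifts of 0.1 to 0.5 paired-difference SD. Drift could equally mask a real effect.

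Manipulation versus rotation remains a valid randomised comparison, subject to carry-over. No washout is described, the documents do not say how long an effect lasts, and a period term does not remove unequal carry-over.

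**What to change.** State in the SAP and the report:

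1. Both neutral contrasts are before-after changes. Neither the omnibus test nor the VA position main effect is read as a manoeuvre effect. Neutral was always first, and series order differed between the neutral and later blocks.
2. Causal inference rests on manipulation versus rotation, with carry-over acknowledged as possible.
3. That contrast is fitted with participant, condition and period (0 for neutral, −0.5/+0.5 for the first/second post-manoeuvre scan); the VA model keeps side and condition × side. The unadjusted result and the realised sequence split are reported beside it.
4. The VA position × side interaction may be read as a partial internal check, valid only if drift is equal on both sides.

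**Cost.** Wording and a re-run of existing data, no new scans, and one error degree of freedom. For the paired test under simple randomisation, the period term loses about 2 to 2.5 power points at drift 0 to 0.1 and about 1 at 0.2. It gains about 1 at 0.3 and 7 at 0.5. With no drift it loses about 4 points at a 7/13 split and 7 at 6/14. The neutral contrasts remain unidentified after these changes; no re-analysis of these data can alter that.

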RE: "Changes in Vertebral Artery and Cerebral Hemodynamics Following Various Head Positions & Cervical Manipulation in Patients with Chronic/Recurrent Neck Pain."

Co-Investigators:

[name], BSc DC

[name], DC PhD

[name], DC PhD

[name], DC PhD

[name]

[name]

To whom it may concern,

We thank you for your consideration of this work. Please find below 4 pages detailing the methods and procedures of the study.

Sincerely,

[name], BSc, DC

Methods

Participants

Twenty patients were recruited from the campus-teaching clinic located at the Canadian Memorial Chiropractic College. Included were adults aged 18 years and older with chronic grade II/III mechanical neck pain that had been prescribed cervical manipulation for treatment of their condition. Patients with a history of neck pain with associated arm pain within the last 6 months; any current or history of neurologic symptoms including facial or extremity weakness, abnormal sensation to the face, body, or extremities, uncontrolled movements, abnormal gait, dizziness, unexplained nausea/vomiting, difficulty with speaking or swallowing; history of new or severe (Visual Analogue Scale >6) headaches in the last 3 months; any contraindications to MRI; or any history of using drugs that affect blood flow such as Warfarin, or anti-coagulants were excluded. All participants refrained from vigorous physical activity, alcohol, and caffeine one day before commencement of the study.

The study was approved by the local ethics committees of St. Joseph's Healthcare Hamilton at McMaster University in Hamilton, Ontario, and Canadian Memorial Chiropractic College in Toronto, Ontario. Written informed consent was obtained from all participants before the study commenced. Data were collected at the Imaging Research Centre, Hamilton, Ontario. The study was registered with www.clinicaltrials.gov, NCT02667821.

Test Protocols

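### The ASL and BOLD group maps have a single significance rule, alpha 0.05 at an unstated level with no control over voxels; applied per voxel, it makes about 5% of any null search volume positive

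*Combined protocol and SAP*

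**What the plan says.** All of the relevant text is in the Data Analysis section of the combined protocol and SAP.

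- **Group test:** "Group analysis was accomplished using a 1-way within subject 3D-ANOVA, with the one factor being neck position". The factor has three levels: neutral, maximum voluntary rotation and manipulation (CSM).
- **Follow-up tests:** "Post hoc testing included contrasts between neutral, maximum voluntary rotation and CSM, and also a contrast between maximum voluntary rotation and CSM". The natural reading is three pairwise contrasts, although the first clause does not list them.
- **Decision rule:** "Statistical significance was defined as anything lower than an alpha value of 0.05". This is the only rule for these maps.
- **Image preparation:** for BOLD, "A 5mm FWHM Gaussian spatial smoothing filter was applied"; for ASL, "spatial blurring with a 5mm FWHM Gaussian convolution kernel". The grid is given only for BOLD: "functional data resampled to a 2mm isometric grid".
- **Scope of the BOLD question:** "Functional connectivity within the default mode network (DMN) was assessed using the AFNI plugin InstaCorr". No mask or search volume is given for the group test. For ASL, no restriction of the search is mentioned at all.

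Two other significance rules appear, and neither covers these maps. One is the .05 level for the repeated-measures ANOVA of vertebral artery flow and velocity. The other is the Bonferroni level of 0.01 for the t-tests between raters on the perception scale.

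**The concern.** A 3D-ANOVA produces a test at every voxel, so a threshold has a known error rate only if the plan says what unit it applies to and how the number of voxels is handled. This plan says neither. The rest of the image processing is described closely (atlas, filter cut-offs, seed coordinates, smoothing kernel), and a correction is named for the rating scale. Smoothing, filtering and outlier censoring are preparation steps; they do not control error.

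Cerebral hemodynamics is in the study title, and these maps are the only analysis of brain perfusion and connectivity. If 0.05 is a per-voxel threshold, a study with no true effect would still be expected to show significant regions after rotation or manipulation.

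**Working it through.** The plan gives no error-rate or power figure for the imaging analysis, so there is none to reproduce.

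**Inputs from the documents**
- Alpha 0.05; three conditions; 5 mm FWHM smoothing for both modalities (Data Analysis).
- 20 participants: "Twenty patients were recruited from the campus-teaching clinic" (Participants). Error degrees of freedom: (20 − 1) × (3 − 1) = 38.
- 2 mm grid for functional data, so one voxel is 2 × 2 × 2 = 8 mm³ (0.008 mL). The ASL grid after warping is not stated.

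**Assumptions**
- Search volume: 100 mL (a small mask) to 1.5 L (whole brain).
- Total image smoothness: at 5 mm, the applied kernel is taken as the whole smoothness. Values of 10 and 15 mm are used as a sensitivity check, because intrinsic smoothness adds to the kernel.

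**Step 1. Expected null-positive volume if 0.05 is per voxel.** The expected count is 0.05 × volume ÷ 0.008 mL. Spatial correlation changes the spread and clustering, but not this mean.

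| Assumed search volume | Voxels at 2 mm | Expected false-positive voxels | Volume |
|---|---|---|---|
| 100 mL | 12,500 | 625 | 5 mL |
| 500 mL | 62,500 | 3,125 | 25 mL |
| 1,200 mL | 150,000 | 7,500 | 60 mL |
| 1,500 mL | 187,500 | 9,375 | 75 mL |

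The 5% share holds on any grid and so covers ASL too. The voxel counts apply to the functional data.

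**Step 2. Chance of at least one false positive per map.** A rough approximation is 1 − 0.95^R, with R = volume ÷ FWHM³.
- 100 mL at 5 mm: R = 100,000 ÷ 125 = 800, giving more than 0.999.
- 100 mL at 10 mm: R = 100,000 ÷ 1,000 = 100, giving 0.994.
- 100 mL at 15 mm: R = 100,000 ÷ 3,375 = 29.6, giving 0.78.
- 1.2 L at 15 mm: R = 1,200,000 ÷ 3,375 = 355.6, giving more than 0.999.

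**Step 3. Null simulation.** Gaussian noise for 20 participants under 3 conditions was tested with the within-subject F(2, 38) and pairwise contrasts at p < 0.05 on a 2 mm grid.
- 512 mL volume, 40 runs per smoothness. The mean share of positive voxels in the F map was 5.1% (range 4.7 to 5.7%) at 5 mm and 4.9% (4.0 to 6.7%) at 10 mm. Every F map had a false positive. The median largest false cluster was about 90 voxels (90 × 8 mm³ = 0.7 mL) at 5 mm and 349 voxels (2.8 mL) at 10 mm.
- Assumed 1.33 L brain (166,256 voxels), 5 mm, 200 runs. All 200 F maps and all 200 contrast maps were positive. The mean was 8,322 false voxels per contrast, against 0.05 × 166,256 = 8,313 expected. In a mask of 10% of that volume, the mean was 834 and the minimum 618.
- The same 10% mask at 10 and 15 mm, 100 runs each. Every map was still positive, so the approximation in step 2 errs on the low side.

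**Step 4. Several contrasts at one voxel.** With three pairwise contrasts and pooled error, the chance that any is false-positive is P(studentized range of 3 means, 38 df > √2 × t(0.975, 38)) = 0.120. Paired t-tests in the simulation gave 12.6% at 5 mm and 12.4% at 10 mm. Reading contrasts only after a positive F caps this at 0.05 per voxel under the global null, but leaves the number of voxels unaddressed.

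**Step 5. The other branch.** If 0.05 is already a map-level rate, the false-positive chance is 5% per map and at most 3 × 0.05 = 15% over three unadjusted contrasts.

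**The case against.** The strongest reply is that the text does not say the maps were uncorrected. Defining significance as below 0.05 is also compatible with a corrected p-value, and the section never calls the group test or its threshold voxelwise. This stands. A reader might infer that an uncorrected threshold was in fact used; the documents show only that no correction is stated.

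A reader might also infer that every positive region in these maps is noise. That goes too far: a region with a very small p-value or a large extent could survive a proper correction, and re-thresholding would show it. What cannot be relied on is a region reported only because it passes uncorrected 0.05.

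Three further replies carry less weight.
- The BOLD search may have been confined to the default mode network. No such mask is stated, and a mask of 10% of the assumed brain still gave false positives in every simulated map.
- The label post hoc may mean that contrasts follow a positive F. All the null F maps were themselves positive.
- The number and size of false clusters depend on total smoothness and on the cluster definition chosen, neither of which the plan gives. That is correct, so the conclusion rests on the 5% share and not on cluster counts.

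**Conclusion.** Wrong as written. The ASL and BOLD maps have one decision rule, it has no stated level, and no control over voxels or search mask accompanies it. On the natural per-voxel reading, about 5% of any null search volume is positive, and at least one false-positive region per map is almost certain at the stated smoothing.

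The absence of a stated correction is certain; per-voxel use is inferred. The 5% share needs no assumption beyond that inference. The voxel counts depend on the assumed search volumes and the 2 mm functional grid, and the multiple-contrast figures on there being three pairwise contrasts. If a map-level correction was applied, the defect is one of reporting, apart from the contrasts if they were left unadjusted. The vertebral artery ANOVA is a separate analysis, and nothing here bears on it.

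**What to change.** Replace the significance sentence with one map-level rule, for example: *ASL and BOLD group maps are tested over a stated mask for each modality, fixed independently of the condition contrasts, with family-wise error held at 0.05 per map by a cluster-extent threshold (cluster-forming p stated, smoothness estimated from the residuals); contrasts are adjusted for their number.* With three contrasts, a Bonferroni adjustment would be 0.05 ÷ 3 = 0.0167 per contrast map. The extent threshold cannot be computed from the documents, because total smoothness, mask and cluster-forming p are not given. Another valid family-wise method would serve, provided that one is chosen and named.

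Then re-threshold the existing maps and label any uncorrected map as descriptive. Because the document describes the analysis in the past tense, new wording cannot count as pre-specification, so the report should say which rule produced the original maps. If a map-level correction was already used, one sentence giving its level, mask and method is enough, with the handling of the contrasts made explicit.

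**Cost:** a wording change and re-thresholding in AFNI, with no new data. Fewer regions will be positive, and with 20 participants sensitivity falls, so the absence of a surviving region should not be read as evidence of no change.
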